6.3 Exclusion Criteria

Pregnant, breastfeeding, or unwilling to practice birth control during participation in the study; Presence of a condition or abnormality that in the opinion of the Investigator would compromise the safety of the patient or the quality of the data; Diagnosis of diabetes mellitus (type I or type II); Current SGLT-2 inhibitor administration at the time of screening or SGLT-2 inhibitor administration within the last year prior to screening; Vulnerable populations including incarceration status; Anticipation of pregnancy during the study duration; Unable to give informed consent; Non-English primary language; pregnancy, lactation, or child- bearing age without birth control devices; Serious illness likely to cause death within the next 5 years.

7 CONCURRENT MEDICATIONS

All subjects should be maintained on the same medications throughout the entire study period, as medically feasible, with no introduction of new chronic therapies. However, patients will who are on medications commonly used to treat diabetes, such as but not limited to insulin, metformin, and glipizides will not be allowed to continue these while on study. These medications may interfere with the action of SGLT-2 inhibitors by altering the manner in which the body metabolizes and regulates glucose. Participants will also be asked to stop any medications commonly used to treat cystinuria they may be taking for the duration of the study as well: thiola, penicillamine, alpha lipoic acid.

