CRITERIA	history of previous cystine kidney stones; and being able and willing to provide consent Exclusion Criteria: prior diagnosis of diabetes mellitus (type I or type II); current SGLT-2 inhibitor administration at the time of screening; SGLT-2 inhibitor administration within the last year prior to screening; vulnerable populations including incarceration status; anticipation of pregnancy during the study duration; unable to give informed consent; non-English primary language; pregnancy, lactation, or child- bearing age without birth control devices; and serious illness likely to cause death within the next 5 years.
TEST PRODUCT, DOSE, AND ROUTE OF ADMINISTRATION	Dapagliflozin 10 mg administered orally once daily for 4 weeks
CONTROL PRODUCT, DOSE AND ROUTE OF ADMINISTRATION	None
DURATION OF SUBJECT PARTICIPATION AND DURATION OF STUDY	Subjects will be on study for up to 6 weeks 
• Screening: 1 week to determine eligibility• Treatment: 4 weeks after the initial visit (Day 0)• Follow-up: 1 week after the last visit (Day 28)
CONCOMMITANT MEDICATIONS	Allowed: The participants will be allowed to continue any medications they are currently taking with the exception of those listed below under “prohibited”. Importantly, patients will be allowed to continue potassium citrate as this is an important mainstay of cystinuria treatment as discontinuation may lead to clinically significant cystine stone formation. Prohibited: Medications commonly used to treat diabetes, such as but not limited to insulin, metformin, and glipizides. These medications may interfere with the action of SGLT-2 inhibitors by altering the manner in which the body metabolizes and regulates glucose. Medications commonly used to treat cystinuria: thiola, penicillamine, alpha lipoic acid
EFFICACY EVALUATIONS	Efficacy in this study will be determined by utilizing mass spectrometry to analyze for the presence of sulfur in the urine before and after initiation of therapy with SGLT-2 inhibitor in our patients with cystinuria. Urinary cystine levels on 24-hour urine collection will also be measured.
PRIMARY ENDPOINT	Quantitative urinary sulfur via inductively coupled plasma optical emission spectroscopy (ICP-OES) in freshly voided urine

SGLT2-02, [name]

OTHER EVALUATIONS	

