SAFETY EVALUATIONS	After participants are enrolled at 1 week during the treatment period, a study coordinator will contact each participant to check compliance, tolerability, and side effects with SGLT-2 inhibitor therapy. Any concern for a potential adverse event will be reviewed by the study investigators. Patient clinical care will continue as per the current standard for the duration of this study. Tolerability and side effects will be reviewed at each of the two clinic visits. All reported adverse events will be reviewed by the study investigators. Depending on the severity of the adverse event, the participant may be advised to stop SGLT-2 inhibitor therapy intake if it is determined that SGLT-2 inhibitor therapy is the cause. Most common AEs noted include male and female genital yeast infections, UTI, increased urination, discomfort with urination.
PLANNED INTERIM ANALYSES	When approximately 50% of patients have completed the study through Visit 2, an interim analysis for safety will be conducted. Serious adverse events will be monitored on an ongoing basis throughout the study.
STATISTICS Primary Analysis Plan	The primary efficacy endpoint will be assessed by comparing the qualitative and quantitative differences between the mass spectrometry output data between the participants' freshly voided urine at the initial visit and at the follow up visit after initiation of SGLT-2 inhibitor therapy, specifically examining the quantitative sulfur content between the two samples as a surrogate for cysteine in the urine.
Rationale for Number of Subjects	This is a preliminary proof of concept study designed to show only that administration of SGLT-2 inhibitor medications alter the excretion of cystine in the urine of patients with documented cystinuria. If initial analyses are promising, further investigation will be undertaken to draw further meaningful, statistical conclusions on the efficacy of this medication.

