Two primary factors known to affect the solubility of cystine include are cystine concentration and pH.⁷ Therefore, the current mainstays of therapy include aggressive hydration to 2.5 to 3 liters of fluid intake daily, lowering of dietary sodium intake, urinary alkalinization to pH >7.0, and thiol derivative medications to bind urinary cystine to reduce urinary cystine concentrations to less than 250 mg/l, the level above which cystine becomes insoluble in urine.⁸ Thiol derivatives in current use including D-penicillamine and alpha-mercaptopropionylglycione increase the solubility of cystine by forming more soluble mixed amino acid-disulfide products. However, these medications are difficult to tolerate due to their side effect profiles and, therefore, compliance is poor.⁹ Furthermore, the medications require regular monitoring of complete blood count, liver enzymes, and urinary protein excretion. In our own kidney stone clinic population, even when compliance is high, cystinuric patients taking D-penicillamine and alpha-mercaptopropionylglycione often continue to form recurrent cystine stones. It is not surprising that because cystinuria is a lifelong disease and current medical management is difficult to achieve and not very effective, these individuals have frequent stone recurrences and a higher risk of kidney loss compared to the average calcium oxalate stone former.¹⁰ Therefore, additional well-tolerated and effective medical therapies to treat cystinuria are desperately needed.

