1.1 Overview of Clinical Studies

Sodium-glucose cotransporter 2 (SGLT2), expressed in the proximal renal tubules, is responsible for the majority of the reabsorption of filtered glucose from the tubular lumen. Dapagliflozin is an inhibitor of SGLT2. By inhibiting SGLT2, dapagliflozin reduces reabsorption of filtered glucose and lowers the renal threshold for glucose, and thereby increases urinary glucose excretion. Dapagliflozin also reduces sodium reabsorption and increases the delivery of sodium to the distal tubule. This may influence several physiological functions including, but not restricted to, lowering both pre-and afterload of the heart and downregulation of sympathetic activity.

SGLT2-02, [name]

Increases in the amount of glucose excreted in the urine were observed in healthy subjects and in patients with type 2 diabetes mellitus following the administration of dapagliflozin. Dapagliflozin doses of 5 or 10 mg per day in patients with type 2 diabetes mellitus for 12 weeks resulted in excretion of approximately 70 grams of glucose in the urine per day at Week 12. A near maximum glucose excretion was observed at the dapagliflozin daily dose of 20 mg. This urinary glucose excretion with dapagliflozin also results in increases in urinary volume. After discontinuation of dapagliflozin, on average, the elevation in urinary glucose excretion approaches baseline by about 3 days for the 10 mg dose.

Following oral administration of dapagliflozin, the maximum plasma concentration (Cmax) is usually attained within 2 hours under fasting state. The Cmax and AUC values increase dose proportionally with increase in dapagliflozin dose in the therapeutic dose range. The absolute oral bioavailability of dapagliflozin following the administration of a 10 mg dose is 78%. Administration of dapagliflozin with a high-fat meal decreases its Cmax by up to 50% and prolongs Tmax by approximately 1 hour, but does not alter AUC as compared with the fasted state. These changes are not considered to be clinically meaningful and dapagliflozin can be administered with or without food.

Overview of Clinical Studies of FARXIGA for Type 2 Diabetes

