4 STUDY DESIGN

4.1 Study Overview

This is a single center, proof of concept prospective cohort trial designed to assess the effect of daily oral administration of dapagliflozin 10 mg on cystine formation in freshly voided urine. Ten subjects are planned, each with previously diagnosed cystinuria and without current treatment except with potassium citrate medication.

SGLT2-02, [name]

Each subject will have an initial visit during which screening data will be reviewed to determine subject eligibility. Subjects who meet all inclusion criteria and none of the exclusion criteria will be entered into the study. Consent will be obtained as well as an initial examination and collection/analysis of freshly voided urine with mass spectrometry to serve as a baseline. The therapy under investigation, dapagliflozin 10 mg, will then be administered orally to each participant daily for four weeks, at which time each subject will return for a second visit for an analysis of freshly voided urine using mass spectrometry. The different urine collections will be compared and analyzed for differences with the prescribed therapy. No placebo will be used during this proof-of-concept study.

Total duration of subject participation will be up to six weeks. Total duration of the study is expected to be six weeks.

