14.3 Analysis of Primary Endpoint

The primary endpoint will be analyzed through quantitative comparison between the baseline urine mass spectrometry analysis and the treatment urine mass spectrometry analysis.

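### Section 7 keeps only medications constant, and nothing records fluid or sodium intake or the conditions of the void, so a shared change in drinking would be counted as drug effect if sulfur concentration is compared

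*Combined protocol and SAP*

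**What the plan says.** Section 7 (Concurrent Medications) sets the stability rule: "All subjects should be maintained on the same medications throughout the entire study period, as medically feasible, with no introduction of new chronic therapies". It then makes exceptions for diabetes drugs and for thiol-type cystinuria drugs and alpha lipoic acid, which are stopped. It does not mention fluid, salt or other diet.

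Section 1 (Background) gives cystine concentration as one of two primary factors in solubility. Its list of mainstays of therapy begins with "aggressive hydration to 2.5 to 3 liters of fluid intake daily, lowering of dietary sodium intake", ahead of alkalinization and thiol drugs.

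The synopsis defines the primary endpoint as "Quantitative urinary sulfur via inductively coupled plasma optical emission spectroscopy (ICP-OES) in freshly voided urine". The analysis is described as "specifically examining the quantitative sulfur content between the two samples as a surrogate for cysteine in the urine", and Section 14.3 as a "quantitative comparison between the baseline urine mass spectrometry analysis and the treatment urine mass spectrometry analysis". No unit, creatinine or volume correction, test or significance level is given. Section 4.1 adds: "No placebo will be used during this proof-of-concept study".

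The eligibility criteria, the visit lists (10.1 and 10.2) and Appendix 1 neither record intake nor fix the time of day or fasting state of the void. The diary in Section 8.6 covers dosing dates and adverse events. Section 9.2.1 includes specific gravity in the urinalysis, which is done at both visits, but no analysis uses it. The synopsis mentions 24-hour urine cystine, but no visit schedules it.

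**The concern.** The protocol accepts that co-treatments should stay the same, but applies this to drugs only. By its own account, two non-drug measures acting on the same target are left free and unrecorded.

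The whole efficacy result is a within-subject difference between a Day 0 and a Day 28 sample. With no control arm, anything that moves the subjects in a common direction between those days goes into the estimate alongside the drug. Subjects know that they are in a stone study, and the synopsis lists increased urination as a common adverse effect, so a common change in drinking is plausible. It is an inference, not something the documents report.

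Section 14 leaves a detailed SAP to be written before the final analysis. That SAP could still fix the unit and the test. It could not recover intake that was never recorded.

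**Working it through.** **Is there a plan figure to reproduce?** No. Section 14.5 gives ten subjects with no significance level, power, effect size or SD. What follows illustrates size and does not check a stated calculation.

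**Inputs from the documents**
- Ten subjects, each compared with themselves (Section 14.5 and synopsis).
- Fluid intake of 2.5 to 3 L/day (Section 1). This is a treatment target, used here only as a scale for a change in drinking.
- No control arm (Section 4.1).

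**Assumptions**
- Sulfur is compared as a concentration.
- Daily sulfur excretion does not change, and the drug has no effect.
- Urine volume moves in proportion to intake.
- All ten subjects shift by the same amount.
- The test is a paired t-test on log concentration, one-sided 2.5%.
- The SD of the log change is 0.2 to 0.4.

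**Step 1: dilution.** The concentration ratio is V0/V1 = 2.5/3.0 = 0.833, a fall of 16.7%. On the log scale, ln(0.833) = -0.182. Half of that is -0.091, a fall of 1 - exp(-0.091) = 8.7%.

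**Step 2: chance of a false significant fall.** The noncentrality is |shift| x sqrt(10) / SD. The probability is that of a noncentral t with 9 degrees of freedom exceeding 2.262.

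| SD of log change | Full shift: noncentrality | Full shift: chance | Half shift: noncentrality | Half shift: chance |
|---|---|---|---|---|
| 0.2 | 2.88 | 73% | 1.44 | 25% |
| 0.3 | 1.92 | 40% | 0.96 | 14% |
| 0.4 | 1.44 | 25% | 0.72 | 9% |

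With no shift the rate is 2.5%.

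**Step 3: the same question with another noise scale.** Set the SD of the log difference to sqrt(2) x sqrt(ln(1 + CV²)), with an assumed within-subject CV and a two-sided 5% test. The full shift is then significant 68%, 45%, 24%, 16% and 12% of the time at CVs of 15%, 20%, 30%, 40% and 50% (log SDs 0.21, 0.28, 0.42, 0.55 and 0.67). The two scales agree where they overlap. The noisier the void, the smaller the inflation.

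**Step 4: unsystematic changes.** If some subjects drink more and others less, with mean log change zero, the variation goes into the SD. The error rate stays near nominal and sensitivity falls. Only a shift in a common direction biases the estimate.

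**Step 5: would steady intake be enough?** No. Section 1.1 states: "This urinary glucose excretion with dapagliflozin also results in increases in urinary volume". It gives no size. An assumed extra 0.2 to 0.6 L/day on 2.5 to 3 L lowers concentration at unchanged excretion by between 1 - 3.0/3.2 = 6% and 1 - 2.5/3.1 = 19%. That dilution occurs even if drinking is perfectly stable, so an intake record cannot stand in for a dilution correction.

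**The case against.** **The figures belong mainly to the missing unit.** Every number above is pure dilution, and a creatinine-type ratio would cancel it. This stands. The figures are conditional on comparing concentration, which the documents neither state nor exclude. What an intake record adds once dilution is corrected is the sodium route and the ability to interpret the result, and neither can be quantified from the documents.

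**The scenario is extreme.** All ten subjects moving from one end of a target range to the other is a strong assumption. At 30% of the log shift and SD 0.3 the rate is about 7.5% against 2.5%. This stands too, so the 73% to 25% is an illustration and not a forecast.

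**A marker already exists.** Specific gravity is measured at both visits, and Appendix 1 lists weight twice. This stands only in part. Section 1.1 reports about 70 g of urinary glucose per day on the drug in type 2 diabetes. Dissolved glucose raises specific gravity, so a Day 28 reading does not measure dilution on the same footing as Day 0. The amount in these subjects, who do not have diabetes, is not stated.

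**A stronger reading is tempting.** A reader might infer that a change in drinking or diet can produce the trial's primary result by itself. The documents do not support that. They define no test, threshold, direction or success criterion, and Section 5.1 words the endpoint partly as the presence or absence of signals, which dilution need not shift in proportion. A reader might also extend the point to dietary protein, but no section links protein to cystine or sulfur. Sodium appears only as cystine therapy, with no stated effect on total sulfur.

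**Conclusion.** The gap is real and cheap to close, but secondary to the missing unit and dilution correction. Medications are the only background factor held constant, intake is not recorded, the void is not standardised, and there is no control arm. If concentration is compared, a shared rise in drinking would be attributed to the drug.

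Under the assumptions listed, a full 2.5 to 3.0 L/day shift in all subjects gives a false significant fall 73% to 25% of the time, and half the log shift 25% to 9%. The test, its level, the SD, the proportionality of volume to intake and the common shift are all assumptions. The documents do not show that such a shift will occur. As planned, though, the investigators could not adequately show that it had not.

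**What to change.** 1. At Visit 1 (after consent, which Sections 9 and 10.1 place ahead of any study activity) and again at Visit 2, record fluid and sodium intake over the preceding 24 hours. Use recall both times, so that a change of method cannot look like a change in intake.
2. Collect both voids under the same conditions, such as time of day, and record them.
3. Report each subject's change in intake beside the primary change, in all subjects. Do not exclude anyone for post-treatment intake. Drinking may respond to the drug's effect on urine volume, and selecting on it among ten people would add a bias of its own.
4. Do not set a fluid or diet rule for this purpose. That is clinical management, and the record serves the analysis without one.
5. Separately, state the unit of the primary endpoint with a dilution correction, for example a creatinine ratio or the 24-hour collection that the synopsis already mentions. Specific gravity alone will not serve. The intake record supplements this and does not replace it.

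Items 1 to 4 cost two CRF lines, a sentence on collection conditions, one listing and a slight burden on subjects. Items 1 and 2 must be in place before the first baseline void.

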7.1 Allowed Medications and Treatments

All medications the participant is on are allowed with the exception of: insulin, metformin, and glipizides. These medications may interfere with the action of SGLT-2 inhibitors by altering the manner in which the body metabolizes and regulates glucose. Participants will also be asked to stop any medications commonly used to treat cystinuria they may be taking for the duration of the study as well: thiola, penicillamine, alpha lipoic acid.

8 STUDY TREATMENTS

8.1 Method of Assigning Subjects to Treatment Groups

All participants will be assigned one treatment which includes daily oral administration of dapagliflozin 10 mg for 1 week duration.

8.2 Blinding

This is a nonblinded proof of concept study.

8.3 Formulation of Test and Control Products

8.3.1 Formulation of Test Product

Dapagliflozin 10mg as prescribed by local pharmacy. No control product is being used.

8.4 Supply of Study Drug at the Site

Participants will be given a prescription for dapagliflozin 10mg to be taken orally daily for 4 weeks by the study PI or his assistant MD.

8.4.1 Dosage/Dosage Regimen

10mg of dapagliflozin will be taken orally once daily for 4 weeks. Participants will be encouraged to take the study tablet in the morning to facilitate consistent bioavailability between participants.

8.4.2 Dispensing

Dapagliflozin will be given to the participant with sufficient quantity for administration at home, with a 4 week supply (28 tablets). At the subsequent visit, remaining pills will be counted and counts recorded to reflect compliance for participants.

8.4.3 Administration Instructions

Dapagliflozin 10 mg is to be taken orally once daily every morning.

8.5 Study Drug Accountability

An accurate and current accounting of the dispensing and return of study drug for each subject will be maintained on an ongoing basis by a member of the study site staff. The number of study drug dispensed and returned by the subject will be recorded on the Investigational Drug Accountability Record. The study monitor will verify these documents throughout the course of the study.

8.6 Measures of Treatment Compliance

Participants will be asked to keep a diary noting the day and date they take their study drug and any adverse events. They will be asked to bring their participant diary to each study visit along with all used and unused study drug containers.

9 STUDY PROCEDURES AND GUIDELINES

A Schedule of Events representing the required testing procedures to be performed for the duration of the study is diagrammed in Appendix 1.

Prior to conducting any study-related activities, written informed consent and the Health Insurance Portability and Accountability Act (HIPAA) authorization must be signed and dated by the subject or subject's legal representative. If appropriate, assent must also be obtained prior to conducting any study-related activities.

9.1 Clinical Assessments

9.1.1 Concomitant Medications

All concomitant medication and concurrent therapies will be documented at Visit 1 and at Visits 28. Dose, route, unit frequency of administration, and indication for administration and dates of medication will be captured.

9.1.2 Demographics

Demographic information (date of birth, gender, race) will be recorded at Visit 1.

9.1.3 Medical History

Relevant medical history, including history of current disease, other pertinent respiratory history, and information regarding underlying diseases will be recorded at Visit 1.

9.1.4 Physical Examination

A complete physical examination will be performed by either the investigator or a sub-investigator who is a physician at the initial visit. Qualified staff (MD, NP, RN, and PA) may complete the abbreviated physical exam at all other visits. New abnormal physical exam findings must be documented and will be followed by a physician or other qualified staff at the next scheduled visit.

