11 ADVERSE EXPERIENCE REPORTING AND DOCUMENTATION

11.1 Adverse Events

An adverse event (AE) is any untoward medical occurrence in a clinical investigation of a patient administered a pharmaceutical product and that does not necessarily have a causal relationship with the treatment. An AE is therefore any unfavorable and unintended sign (including an abnormal laboratory finding), symptom or disease temporally associated with the administration of an investigational product, whether or not related to that investigational product. An unexpected AE is one of a type not identified in nature, severity, or frequency in the current Investigator's Brochure or of greater severity or frequency than expected based on the information in the Investigator's Brochure.

The Investigator will probe, via discussion with the subject, for the occurrence of AEs during each subject visit and record the information in the site's source documents.

Adverse events will be recorded in the patient CRF. Adverse events will be described by duration (start and stop dates and times), severity, outcome, treatment and relation to study drug, or if unrelated, the cause.

AE Severity

The National Cancer Institute's Common Terminology Criteria for Adverse Events (CTCAE) Version 3.0 should be used to assess and grade AE severity, including laboratory abnormalities judged to be clinically significant. The modified criteria can be found in the study manual. If the experience is not covered in the modified criteria, the guidelines shown in Table 1 below should be used to grade severity. It should be pointed out that the term "severe" is a measure of intensity and that a severe AE is not necessarily serious.

Table 1. AE Severity Grading

Severity (Toxicity Grade)	Description
Mild (1)	Transient or mild discomfort; no limitation in activity; no medical intervention or therapy required. The subject may be aware of the sign or symptom but tolerates it reasonably well.
Moderate (2)	Mild to moderate limitation in activity, no or minimal medical intervention/therapy required.
Severe (3)	Marked limitation in activity, medical intervention/therapy required, hospitalizations possible.
Life-threatening (4)	The subject is at risk of death due to the adverse experience as it occurred. This does not refer to an experience that hypothetically might have caused death if it were more severe.

AE Relationship to Study Drug

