11.2.1 Serious Adverse Experience Reporting

Study sites will document all SAEs that occur (whether or not related to study drug) per [UCSF CHR Guidelines](#). The collection period for all SAEs will begin after informed consent is obtained and end after procedures for the final study visit have been completed.

In accordance with the standard operating procedures and policies of the local Institutional Review Board (IRB)/Independent Ethics Committee (IEC), the site investigator will report SAEs to the IRB/IEC.

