12 DISCONTINUATION AND REPLACEMENT OF SUBJECTS

12.1 Early Discontinuation of Study Drug

A subject may be discontinued from study treatment at any time if the subject, the investigator, or the Sponsor feels that it is not in the subject's best interest to continue. The following is a list of possible reasons for study treatment discontinuation:

- Subject withdrawal of consent

SGLT2-02, [name]

- Subject is not compliant with study procedures
- Adverse event that in the opinion of the investigator would be in the best interest of the subject to discontinue study treatment
- Protocol violation requiring discontinuation of study treatment
- Lost to follow-up
- Sponsor request for early termination of study
- Positive pregnancy test (females)

If a subject is withdrawn from treatment due to an adverse event, the subject will be followed and treated by the Investigator until the abnormal parameter or symptom has resolved or stabilized.

All subjects who discontinue study treatment should come in for an early discontinuation visit as soon as possible and then should be encouraged to complete all remaining scheduled visits and procedures.

All subjects are free to withdraw from participation at any time, for any reason, specified or unspecified, and without prejudice.

Reasonable attempts will be made by the investigator to provide a reason for subject withdrawals. The reason for the subject's withdrawal from the study will be specified in the subject's source documents.

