12.3 Withdrawal of Subjects from the Study

A subject may be withdrawn from the study at any time if the subject, the investigator, or the Sponsor feels that it is not in the subject's best interest to continue.

All subjects are free to withdraw from participation at any time, for any reason, specified or unspecified, and without prejudice.

Reasonable attempts will be made by the investigator to provide a reason for subject withdrawals. The reason for the subject's withdrawal from the study will be specified in the subject's source documents. As noted above, subjects who discontinue study treatment early (i.e., they withdraw prior to Visit 2) should have an early discontinuation visit.

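### The follow-up week after Day 28 has no site-initiated contact and lies outside the SAE window, so the rule to follow new exam findings at the next visit cannot operate at Visit 2

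*Combined protocol and SAP*

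**What the plan says.** Section 9.1.4 sets the rule for examination findings: "New abnormal physical exam findings must be documented and will be followed by a physician or other qualified staff at the next scheduled visit".

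Section 10 describes two visits, Visit 1 on Day 0 and Visit 2 on Day 28. Appendix 1 has the same two columns, and the synopsis agrees: "Tolerability and side effects will be reviewed at each of the two clinic visits". Between them, under Safety Evaluations in the synopsis, one week into treatment "a study coordinator will contact each participant to check compliance, tolerability, and side effects with SGLT-2 inhibitor therapy".

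The duration entry in the synopsis gives one week of screening, four of treatment, and then "Follow-up: 1 week after the last visit (Day 28". No visit, call or assessment is attached to that last week there, in Section 10 or in Appendix 1.

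Section 11.2.1 fixes the SAE window: "The collection period for all SAEs will begin after informed consent is obtained and end after procedures for the final study visit have been completed".

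Two other rules deal with follow-up, both for people who stop early. Section 12.1: "If a subject is withdrawn from treatment due to an adverse event, the subject will be followed and treated by the Investigator until" the problem has resolved or stabilized. Section 12.3: "subjects who discontinue study treatment early (i.e., they withdraw prior to Visit 2) should have an early discontinuation visit".

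Sections 9.1.6 and 11.1 require a stop date and an outcome for every adverse event.

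**The concern.** The complete examination at Visit 1 takes place before the drug is prescribed. Visit 2 is therefore the first scheduled examination that can show something new on treatment, and it is also the last. The rule in 9.1.4 has no visit to act on at the point where it is most needed.

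The follow-up week could have filled that role, but it is only a time span. The SAE window closes before it begins. A site that follows the written rules would not initiate any contact in that week, and would have no instruction in 11.2.1 to collect a serious event that starts in it.

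What is at stake is the safety record. For an event still open at Visit 2 the site owes a stop date and an outcome, with no set occasion to learn them. The reactions listed in Section 11.2 include urinary tract infection, ketoacidosis and acute kidney injury, where the course after stopping the drug matters.

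**Working it through.** The plan gives no figure to reproduce here. The check sets the schedule against the follow-up rules, with simple day counts.

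**Site-initiated contacts for a participant who completes treatment**

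| Contact | Day | Source |
|---|---|---|
| Visit 1 | 0 | Section 10.1, Appendix 1 |
| Coordinator contact | about 7 | Synopsis, Safety Evaluations |
| Visit 2 | 28 | Section 10.2, Appendix 1 |
| Any contact in the follow-up week | none named | Synopsis, Section 10, Appendix 1 |

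Total: 2 visits + 1 contact = 3. After Day 28: 0.

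The safety check in Section 5.2 is worded as coming after a one-week treatment period, which does not fit the four weeks stated in most other places. The synopsis puts that check during treatment, so it does not supply a contact in the follow-up week.

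**Does Day 35 fall within planned participation?** Screening 1 + treatment 4 + follow-up 1 = 6 weeks, matching the stated maximum of six weeks. Day 28 + 7 = Day 35 is the end of that period.

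**Where the SAE window ends relative to dosing.** Section 8.4.2 supplies 28 tablets, taken once daily. The start day is not stated, so I take Day 0 or Day 1 as an assumption, with no missed doses.
- Start on Day 0: last tablet on Day 27. Visit 2 is 28 − 27 = 1 day later; Day 35 is 35 − 27 = 8 days later.
- Start on Day 1: last tablet on Day 28. Visit 2 is 28 − 28 = 0 days later; Day 35 is 35 − 28 = 7 days later.

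**How much of the study lies outside the window.** From consent at Visit 1 to the end of follow-up is 35 days. The SAE window covers Day 0 to Day 28. The remainder is 35 − 28 = 7 days, and 7 / 35 = 20% of the time on study after consent.

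**Do the early-stop rules cover a completer?** Section 12.1 applies to someone withdrawn from treatment because of an adverse event. Section 12.3 applies to someone who stops before Visit 2. Someone who takes all 28 tablets and has a new finding on Day 28 meets neither condition. For an early stopper, Visit 2 may itself serve as the next visit, but that does not help with a finding first made at Visit 2.

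**Do the AE and SAE windows agree?** Section 9.1.6 captures adverse events for the whole study. If the study includes the follow-up week, as the six-week total implies, a non-serious event on Day 32 is to be recorded while the SAE section has already closed. The narrower window applies to the more serious events.

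**The case against.** The strongest reply is that other provisions already cover much of this.

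- Section 5.2 gives every participant the coordinator's email address and a 24-hour physician telephone number for the study period, which reasonably includes the follow-up week.
- Section 9.1.6 captures adverse events for the whole study, and the grading in 11.1 extends to laboratory results, "including laboratory abnormalities judged to be clinically significant".
- Section 16.2 requires the IRB to be told of serious or unexpected events during the study. Section 16.5 requires adverse events to be reported to the sponsor and unanticipated problems to the IRB and the sponsor. None of these duties is worded to stop at Visit 2.
- Usual clinical care continues.

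All of this stands. A reader might infer that the protocol leaves a completer with no route to report, and the site with no duty to act, after Day 28. The documents do not support that. But these provisions work only once the participant calls or the site otherwise learns of an event. None schedules a check of a finding that staff made at Visit 2, and none changes the 11.2.1 window.

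A second reply is that the text available has a gap between 11.2.1 and Section 12, where the contents list places 11.4 Medical Monitoring. General rules for following open events could be there. So the broader inference, that the protocol has no rule for following a completer's event to resolution, cannot be drawn. The two-visit schedule and the 11.2.1 wording can be read in full and do not depend on that part.

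Two further inferences are tempting and weak. Section 1.1 says that urinary glucose takes about 3 days to approach baseline after the 10 mg dose, longer than the 0 to 1 day between last tablet and Visit 2. That describes the drug's effect on glucose, not how long an infection or kidney injury takes to settle. And although the Probably category in Table 2 asks for confirmation by stopping or reducing the drug, Possibly does not, nor does Definitely for a previously known toxicity, so causality can still be graded.

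**Conclusion.** The point holds in limited form. No site-initiated contact is assigned after Day 28, the 9.1.4 rule has no visit to act on for findings first made at Visit 2, and the SAE window excludes the protocol's own follow-up week: 7 days per participant, for about ten completers, since Section 12.4 replaces those who withdraw. The documents give no rate of events still open at Day 28, so no expected number of lost outcomes can be stated.

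This concerns the completeness of safety data in a small open-label study of a marketed drug. The primary endpoint is measured at Visits 1 and 2 and is not affected. The conclusion assumes dosing starts on Day 0 or Day 1 and that the part of Section 11 not seen does not itself schedule a contact after Visit 2. It should be corrected because the correction is cheap and uses time already planned.

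**What to change.** 1. Add a coordinator telephone contact at about Day 35 to Section 10 and Appendix 1, using the follow-up week already in the synopsis. Record new adverse events, and the outcome and stop date of any event open at Visit 2.
2. Amend 11.2.1 so that SAE collection runs through that contact.
3. In 9.1.4, have findings first made at Visit 2 followed at the Day 35 contact and then until they resolve or stabilize. If the part of Section 11 not seen here already sets follow-up of open events, cross-refer to it from 9.1.4 instead.

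Cost: one IRB-approved amendment and about ten calls (10 participants × 1), plus a few later calls or chart checks for events still open. No clinic visit is added and participation stays within six weeks.
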